### **Quality of life (QOL) questionnaire**

In addition, we will evaluate the overall QOL (physical function and health status) using the Kidney Disease Quality of Life-Short form (KDQOL-SF) version 1.3. The KDQOL-SF is a self-report questionnaire of 24 items designed for individuals with CKD on MHD. Each answer was scored on a 0 to 100 range; a higher score correlates with a better health state and physical function.

### **Body composition**

We will measure body composition using the bioelectrical impedance analysis (BIA) and skinfold thickness, as previously described. BIA will be measured using a standard single frequency (50 KHz) bioelectrical impedance analyzer. For this purpose, four electrodes will be placed on the foot after cleaning the skin with alcohol pads. A small current (~800 uA) will be passed through the electrodes and the body. Total body water and the percent of body fat will be calculated by the analyzer according to the predetermined regression equations. Mid-upper arm muscle circumference (MUAMC) measured. This estimates the circumference of the bone and muscle portions of the upper arm; which in turn helps estimate body fat. Skinfold calipers (Lange) will be used to measure the tricipital skin folds. The circumference of the upper arm will also be measured.

### **Near-infrared spectroscopy**

Skeletal muscle tissue oxygenation will be measured, when possible, using near-infrared spectroscopy (NIRS), as previously described. For this purpose, a rigid emitter-detector device will be placed over the belly of the quadriceps muscle. The device transmits near-infrared light at two wavelengths (735 and 810 nm) and will detect the reflected light to measure oxygenated hemoglobin and deoxygenated hemoglobin. The regional oxygen saturation, which is a measurement of tissue oxygenation, will be calculated as the ratio of oxygenated hemoglobin to the total hemoglobin. Skeletal muscle oxygenation will be measured before and during the hemodialysis session.

### **Dialysis Recovery Time**

We will ask the patients "How long does it take to recover from a hemodialysis session", as described in a previous study. This information will be collected during the follow-up phone call or the visit at the next regular hemodialysis session. The answer will be recorded in minutes. We will convert the following answers to numbers: 1. One day = 1440 minutes; 2. More than one day = 2160 minutes, or 3. Half-day or next day = 720 minutes

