## 6.0 Study Procedures

### Study protocol

After obtaining consent, study subjects will undergo the following procedures.

**COVID-19 precautions prior to and during visits.** Pre-visit phone call – we will contact the patient before all of their study visits to ask a series of COVID-19-related screening questions. Depending on their answers, we will continue with the study visit or postpone for another time. The patient will be asked to wear a face covering during all portions of their study visits in which they are in the presence of hospital staff. We will also encourage frequent hand washing and/or provide alcohol-based hand sanitizer.

Subjects will participate in a randomized, parallel-group, double-blind, placebo-controlled study in which they will receive two doses of placebo or 300 mg of lanadelumab subcutaneously. Participants will continue their usual medications throughout the study. One week (Day -7) before the administration of the first dose of the study drug, we will conduct a study visit at the hemodialysis unit. During this visit, we will give the participants a physical activity monitor to be worn for at least 5 consecutive days and will obtain baseline blood samples. During a second study visit at the dialysis unit (Day -1), we would obtain a second baseline blood sample one to three days before the administration of the first dose of the study drug. In this visit, we will also measure

muscle oxygenation using near-infrared spectroscopy (NIRS). Patients will be then asked to come to the Vanderbilt Clinical Research Center (CRC) on a non-dialysis day. During this visit (Day 0), we will obtain a detailed history, perform a physical examination, administer a quality of life (QOL) questionnaire, obtain the dialysis recovery time, and evaluate body composition and physical performance. We will then administer the first dose of the study drug and monitor the appearance of any Type I (immediate) hypersensitivity reaction for two hours before discharging patients from the CRC. We will repeat the same protocol, as outlined for Day 0 and administer the second dose of the study drug two weeks later at the CRC (Day 14).

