## **10.0 Statistical Considerations**

### ***a. Sample size***

The primary outcome will be the change in blood pressure during hemodialysis. For this, we will average blood pressure during hemodialysis of three hemodialysis sessions within the second week of treatment. Secondary endpoints will also be recorded during the second week of treatment and will include the number of hypotensive events, frequency of nursing interventions, average of dialysis recovery times, and average symptoms severity score. Based on our preliminary studies with icatibant and assuming a standard deviation of differences of 13.6 mmHg (pooled SD of the delta), a sample size of 16 in each arm will have 80% power to detect a difference in means of -13.7 mmHg, using a paired t-test with a 0.05 two-sided significance level.

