## Appendix A Summary of study procedures

	+/-3 days						+/-4days				
	Day-7	Day -1	Day 0	Day 1	Day 3	Day 13	Day 14	Day 15	Day 17	Day 29	Day 43
CRC visit			X				X				
HD visit	X	X		X	X	X		X	X	X	X
Blood draw PK		X		X	X			X	X	X	X
Blood draw clinical labs	X				X	X			X	X	
Blood draw research labs		X		X				X			X
Serum pregnancy test			X				X				
Drug administration			X				X				
Medical history /PE			X								
QOL questionnaire/ recovery time			X				X				X
Symptoms questionnaire/ BP monitoring log				X	X			X	X	X	X
NIRS		X						X		X	X
Physical performance tests - Body composition***			X				X				X***
Collect dialyzer		X		X	X			X	X	X	X
activity monitor*	X*										X*

\* monitor ends after at least 5 days of consecutive use

\*\*It includes: physical performance tests (six-minute walk test, physical battery, and handgrip strength), bioelectrical impedance analysis, and MUAMC

\*\*\*Physical performance will only include handgrip strength

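### The schedule gives one second-week recovery-time answer, or none, so the planned second-week average cannot be formed, and the question names no session

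*Combined protocol and SAP*

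**What the plan says.** Four places bear on this endpoint.

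- **Section 10.0a, Sample size**, lists recovery time among the secondary endpoints, as an average, and fixes the window: "Secondary endpoints will also be recorded during the second week of treatment". Section 10.0b lists recovery time again, and it is part of the Aim 2 hypothesis.
- **Section 6.0, Dialysis Recovery Time**, gives the wording, "How long does it take to recover from a hemodialysis session", taken from a cited study, and the timing: "This information will be collected during the follow-up phone call or the visit at the next regular hemodialysis session". Long answers are coded 720 minutes (half a day or the next day), 1440 (one day) or 2160 (more than one day).
- **Section 6.0, Study protocol**, puts the item in the Day 0 visit, where staff will "obtain the dialysis recovery time, and evaluate body composition and physical performance". Of that visit it says: "Patients will be then asked to come to the Vanderbilt Clinical Research Center (CRC) on a non-dialysis day". For Day 14: "We will repeat the same protocol, as outlined for Day 0". A last collection is planned at the dialysis unit on Day 43.
- **Appendix A** has a row "QOL questionnaire/ recovery time" marked on Days 0, 14 and 43 only. Dialysis visits are marked on Days -7, -1, 1, 3, 13, 15, 17, 29 and 43. There is no row for a phone call.

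**The concern.** The two timing rules cannot both be followed. A research-centre visit on a non-dialysis day is neither the next regular session nor a phone call. The schedule also does not deliver what the endpoint definition asks for, which is several recovery times from the second week.

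The question adds a second uncertainty, because it names no session and no recall period. A patient with at least six months of dialysis can answer it on Day 14 in two ways:

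- **Usual recovery.** The answer may draw on sessions before the first dose, which would pull both arms towards their untreated level.
- **Recovery from the last session.** The nominal gap from the Day 13 session is one day, so some patients may not have recovered when asked.

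The plan does not say which is meant, so patients and staff may mix them. At stake is how well one Aim 2 endpoint can show an effect. The primary blood pressure endpoint is not touched.

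**Working it through.** **1. The plan's own figures.** No effect size, standard deviation or power is stated for recovery time. The only sample-size figure is for blood pressure: 16 per arm, difference 13.7 mmHg, SD 13.6 mmHg, 80% power, two-sided 0.05. The two-sample normal formula reproduces it: 2 × (1.960 + 0.842)² × (13.6/13.7)² = 15.5, so 16 per arm. Only the 16 per arm is used below.

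**2. Count of answers in the second week** (Appendix A row, Days 0, 14 and 43):

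| Reading of the second week | Days | Answers scheduled |
|---|---|---|
| Second week after dose 1 | 8–14 | 1 (Day 14) |
| Week after dose 2 | 15–21 | 0 (next is Day 43) |

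At three sessions a week, about three sessions fall in either week. An average over sessions needs at least two answers.

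**3. If the answer is usual recovery.** With three sessions a week, 14 × 3/7 = 6 sessions fall between dose 1 and Day 14. Assume the patient weights all recalled sessions equally. The post-dose share is then 6 divided by the number of sessions recalled. For illustration, take the standardised difference that gives 80% power with 16 per arm in a two-sample t-test (1.024), and multiply it by that share:

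| Assumed recall | Sessions | Post-dose share | Power |
|---|---|---|---|
| up to 2 weeks | up to 6 | 100% | 80% |
| 3 weeks | 9 | 67% | 46% |
| 4 weeks | 12 | 50% | 29% |
| 12 weeks | 36 | 17% | 8% |

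**4. If the answer is the last session.** Suppose the Day 13 session ends between 10:00 and 20:00 and the Day 14 visit falls between 08:00 and 14:00. Elapsed time then runs from 12 hours (20:00 to 08:00) to 28 hours (10:00 to 14:00). Assume recovery time is lognormal with median M of 4 to 12 hours and log-SD s of 1.0 to 1.3, so that P(T > t) = 1 − Φ(ln(t/M)/s). Averaging over interview times uniform on 12–28 hours:

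- not yet recovered when asked: 6% to 36%;
- recovery longer than 24 hours: 4% (M = 4, s = 1.0: ln 6 = 1.79) to 30% (M = 12, s = 1.3: 0.693/1.3 = 0.53). These patients would be coded 2160 in any case;
- not recovered when asked, but recovered within 24 hours: about 3% to 8%. Only this group loses a value that the coding would otherwise distinguish.

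**5. How the two readings relate.** Step 3 needs a usual-recovery answer with recall beyond about two weeks, and then there is no cut-off. Step 4 needs a last-session answer, and then there is no pre-dose content. The two losses do not add up for the same answer.

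**The case against.** A reader might infer that the drug effect on recovery time will be diluted or cut off. The documents do not support that. The two mechanisms need opposite readings of the question, nothing is lost to pre-dose recall if patients think back two weeks or less, and every recall length and recovery distribution above is assumed. The power figures also hold the SD fixed and apply to Day 14 only: by Day 43 a four-week recall is wholly post-dose.

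A reader might also infer that the question itself is faulty. The plan takes it from a cited study, and Section 1.0B describes the measure as validated in haemodialysis patients. That source is not available here, so the published wording cannot be judged, and replacing it outright would cost comparability. The instruction to ask at a call or the next session also points towards one particular session.

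Three further points are fair.

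- One day after dialysis is only the nominal gap. The visit labelled Day -1 may fall "one to three days before the administration of the first dose of the study drug", and Appendix A allows visit windows.
- The average in Section 10.0a could mean the mean across patients, for which one answer each would do. But the same section averages the primary endpoint over three second-week sessions, and even the looser reading leaves no answer if the week follows dose 2.
- Both arms are asked identically under blinding, so the issue is lost sensitivity in an unpowered secondary endpoint, not bias between arms.

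What stands is the conflict between the two timing rules and the shortage of second-week answers. Neither depends on an assumption about recall or recovery.

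**Conclusion.** The concern holds as a conflict between sections and a gap in the schedule. Under Appendix A the second week holds one recovery-time answer per patient, or none, so an average over sessions cannot be formed. The rule of asking by call or at the next session is not carried into the schedule on Days 0 and 14.

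The unnamed session makes the Day 14 answer ambiguous, with two alternative risks: pre-dose content, or an interview before recovery is complete. Their size cannot be fixed from the documents. The power range of 80% down to 8% and the 3–8% of lost values are illustrations under stated assumptions. The matter is worth correcting because the remedy is cheap, but it concerns a secondary endpoint only.

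**What to change.** Reconcile Section 6.0 (Study protocol and Dialysis Recovery Time), Section 10.0a and Appendix A:

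1. State which days are the second week, and define the endpoint by the date of the session, not the date of the answer.
2. Add a question on how long recovery from the last dialysis session took, asked at dialysis visits already scheduled. For Days 8–14, use Day 13 (about the preceding session) and Day 15 (about the Day 13 session, noting that this interval includes the second dose on Day 14). For the week after dose 2, use Day 17 (about the Day 15 session). A second value in that week would need the follow-up call to be put into Appendix A; otherwise, define the endpoint as a single value.
3. Use Day -1 for the pre-dose value and Days 29 and 43 for later values.
4. Code a patient who has not recovered by that visit as more than one day (2160 minutes), which the existing codes already allow.
5. Keep the cited general question on Days 0, 14 and 43 as a descriptive item, which preserves comparability with the published measure.

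The cost is one extra question at existing visits and revised marks in Appendix A. No new visit or procedure is needed, unless the call is adopted.

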### **Symptoms questionnaire**

We will conduct a post-dialysis symptoms questionnaire at the next regular dialysis session at the Vanderbilt Dialysis Clinic, as previously described. The symptoms will include, but not limited, to complaints associated with a reduction in blood pressure such as cramps, dizziness, nausea, vomiting, yawning. We will score the severity of the symptoms using a scale from 0 to 4 (0=none, 1=minor, 2=mild, 3= moderate, 4=severe).

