The next two consecutive dialysis treatments after each drug administration (days 1 and 3, and days 15 and 17), we will conduct follow-up visits at the dialysis unit to collect information regarding symptoms after discharge from the CRC. During these visits, at the end of every hemodialysis session, we will also inquire, through a standardized questionnaire, about the presence of any symptoms associated with hypotension. This questionnaire will include symptoms such as cramps, dizziness, nausea, and will be scored according to the severity from 0 to 4 (none to severe). We will also collect blood samples at the dialysis unit for pharmacokinetics and special laboratory analysis. During the six-week length of the study, we will monitor the occurrence of DIH episodes and changes in blood pressure in every dialysis session. For this purpose, we will use the dialysis clinic blood pressure monitor logs. We will also conduct two additional visits at the dialysis units (Day 29 and 43) to draw blood, administer the symptomatology questionnaire, and measure blood flow with NIRS. In the final hemodialysis visit (day 43) we will also give the patients an activity monitor that will be collected after five consecutive days of continuous use. During this last visit, we will also administer the QOL questionnaire, obtain the dialysis recovery time, and perform body composition and physical performance tests (except for the six-minute walk test). Details of the study protocol can be found in Figure 5, Tables 1 and 2, and Appendix 1

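### The symptoms questionnaire has two conflicting timing rules, and the schedule cannot supply the planned second-week average of recovery times

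*Combined protocol and SAP*

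**What the plan says.** **Symptoms.** In Section 6.0, the Study protocol subsection describes the dialysis visits on Days 1, 3, 15 and 17 and says that "at the end of every hemodialysis session, we will also inquire, through a standardized questionnaire". It adds two later visits with the questionnaire, on Days 29 and 43. The Symptoms questionnaire subsection gives another time: "We will conduct a post-dialysis symptoms questionnaire at the next regular dialysis session". Both use a 0-to-4 severity scale, and both name cramps, dizziness and nausea. Table 1 lists a single symptoms questionnaire. Appendix A has a single row for it, marked on Days 1, 3, 15, 17, 29 and 43, and does not say which session a form describes.

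**Recovery time.** The Dialysis Recovery Time subsection says "This information will be collected during the follow-up phone call or the visit at the next regular hemodialysis session". The Study protocol subsection and Table 2 instead collect it at the research-centre visits on Days 0 and 14, and the Study protocol subsection collects it again at the Day 43 dialysis visit. The Appendix A row "QOL questionnaire/ recovery time" is marked on those three days only.

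**Endpoints.** Section 10.0a records the secondary endpoints in the second treatment week. They include an "average of dialysis recovery times" and a mean symptom severity score. It does not say which forms, or which timing rule, feed the score.

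**The concern.** Staff who follow one subsection and staff who follow the other would record different dialysis sessions under the same visit label. If the form does not carry the date of the session it describes, this cannot be repaired after collection. Near a dose it matters which session was meant, because the preceding session can lie on the other side of that dose.

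Recovery time raises a separate question: whether the visits can produce the summary that the endpoint names.

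Symptoms and recovery time are the substance of Specific Aim 2, so both endpoints need to be unambiguous before data are collected.

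**Working it through.** The plan states no figure on this point, so the check is made on the visit calendar.

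**Inputs.**
- Dialysis three times a week (Section 4.0).
- Dose 1 on Day 0, a non-dialysis day, and dose 2 on Day 14 (Section 6.0).
- Dialysis study visits on Days -7, -1, 1, 3, 13, 15, 17, 29 and 43 (Appendix A).
- Forms on Days 1, 3, 15, 17, 29 and 43 (Appendix A).

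**Calendar (assumption).** A regular weekly pattern through Days -1, 1 and 3 gives sessions on Days 6, 8, 10, 13, 15, 17, 20, 22, 24, 27, 29, 31, 34, 36, 38, 41, 43 and 45. It matches every questionnaire day and Day 13. Nominal Day -7 is off this pattern, but it carries no form. Days 6, 20, 27, 31, 41 and 45 are inferred, and visit windows may move them.

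**Mapping.** The next-session rule can be laid on Appendix A in two ways. In reading A the marked day is the day of asking. In reading B it is the session described.

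| Marked day | End-of-session rule describes | Reading A describes | Reading B is asked on |
|---|---|---|---|
| 1 | Day 1 | Day -1, before dose 1 | Day 3, study visit |
| 3 | Day 3 | Day 1 | Day 6, no study visit |
| 15 | Day 15 | Day 13, before dose 2 | Day 17, study visit |
| 17 | Day 17 | Day 15 | Day 20, no study visit |
| 29 | Day 29 | Day 27 | Day 31, no study visit |
| 43 | Day 43 | Day 41 | Day 45, no study visit |

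**Counts.**
- End-of-session rule: 6 of 6 forms describe a session after dose 1, and 6 of 6 have a study visit.
- Reading A: 1 of 6 describes a session before any dose; 6 of 6 have a study visit.
- Reading B: 6 of 6 describe a session after dose 1; 2 of 6 have a study visit, so 6 - 2 = 4 do not.

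**Endpoint window for symptoms.**
- If the second week means Days 8–14, the sessions are Days 8, 10 and 13 and no form is marked. Only reading A describes a session inside it: the Day 15 form, about Day 13.
- If it means the week after dose 2, the marked forms are Days 15 and 17. Under reading A these describe Days 13 and 15, both after dose 1.

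**Endpoint window for recovery time.** The scheduled answers are Days 0, 14 and 43. Days 8–14 contain one (Day 14). Days 15–21 contain none. Counting Day 14 as the start of the week after dose 2 gives one, and in the visit order of Section 6.0 it is obtained before that dose is given. Every version therefore has at most one answer, against three dialysis sessions in the week.

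**Place of collection.** Days 0 and 14 are research-centre visits off dialysis, which is not what the Dialysis Recovery Time subsection describes. Appendix A lists no follow-up phone call. The only call that Section 6.0 describes otherwise is the COVID-19 screening call before visits.

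**The case against.** **Two instruments may be meant.** One could cover symptoms in the session and the other symptoms after it. The wording allows this, but Table 1 and Appendix A list only one. If two are intended, one is missing from the schedule.

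**A next session nearly always exists.** This stands. Patients attend three times a week, so in reading B the form can be given. What is missing is a scheduled study visit, not an opportunity.

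**The word average may mean the arm mean.** This is possible. Section 10.0a would then need to say so, and the single value should be named. The conflict over where and when the question is asked would remain.

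**The ambiguity is the same in both arms and does not touch blood pressure.** This stands and limits the weight of the point.

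**End-of-session asking has its own gap.** This stands. If the window is Days 8–14, that rule leaves no form describing a session inside it, so choosing a rule without naming the contributing forms would not be enough.

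**A reader might infer that the treatment effect on both Aim 2 endpoints is diluted, with a calculable loss of power.** The documents do not support this. Section 10.0a does not average over the early forms or over all six, and the Day 1 form lies outside the second week on either meaning. No power is stated for the symptom score. The recovery question asks about recovery in general and names no session, so no answer is shown to belong to the wrong side of a dose.

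**Conclusion.** Two points hold.

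1. The protocol states conflicting timing rules for what its schedule treats as one symptoms questionnaire. The consequence is one of two alternatives. Either the Day 1 form describes a session before dose 1 and the Day 15 form one before dose 2, or the forms for Days 3, 17, 29 and 43 fall due with no scheduled study visit. A reader might infer that both happen together. They cannot, because they come from mutually exclusive readings.
2. The second-week average of recovery times has at most one scheduled answer per participant, and its place of collection is described inconsistently.

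The session counts rest on nominal days and a regular three-times-weekly pattern. The recovery-time count rests on the scheduled days alone. Both points concern secondary endpoints. They should be settled before data collection, but they do not threaten the primary analysis.

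**What to change.** **Symptoms.** Keep one rule: give the form at the end of the session it describes, as the Study protocol subsection has it, and amend the Symptoms questionnaire subsection to match. Record on each form the date of the session it refers to. In Section 10.0, define the second week in study days and name the forms that enter the score. If Days 8–14 are meant, forms must be added there (Day 13 is already a dialysis study visit). If the week after dose 2 is meant, Days 15 and 17 already exist.

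**Recovery time.** Choose one of two options and align the Dialysis Recovery Time subsection, Table 2 and Appendix A with it:
- ask the single question after each session in the defined window, so that an average exists; or
- redefine the endpoint as the Day 14 value adjusted for the Day 0 value, both already scheduled.

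**Cost.** The symptom change is mostly wording plus one date field, with added forms only if Days 8–14 is the window. Symptoms that arise after the patient leaves the unit would no longer enter the symptom score, although recovery time partly covers that period. The first recovery option costs about three one-question contacts per participant. The second costs no extra data but gives up the average, and it reflects the first dose only.
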